## **8.5.2 Active Treatment Period**

### **8.5.2.1 Visit 2 (Infusion 1)**

Infusion 1 must be administered in the timeframe as detailed in [Section 4.2.1](#).

Before infusion 1 of investigational product, hepatic and renal eligibility based on test results from the local laboratory must be confirmed by the investigator, and there must be no suspicion of AKI ([Sections 4.2.1](#) and [8.5.1](#)).

Before the start of infusion, perform the following assessments:

- Prior / concomitant medication review.
- Vital signs.
- Blood sample for central laboratory testing (biochemistry panel and hematology).

- Blood sample for immunogenicity testing (to be retained in the case of a subject experiencing serious hypersensitivity or suspected angioedema during infusion of investigational product infusion).
- Blood sample for parvovirus testing.
- Blood sample for FBR (if subject consented).
- Blood sample for PK / PD assessment (at selected sites).
- AE / SAE monitoring.

Administer the first IV infusion of investigational product (placebo or CSL112) ([Section 6.2](#)).

At the end of the infusion, perform the following assessments:

- AE / SAE monitoring.
- MACE endpoint assessment.
- Blood sample for PK / PD assessment (at selected sites)

### **8.5.2.2 Visits 3, 4, and 5 (Infusions 2, 3, and 4)**

Each infusion of investigational product should be completed as close to the visit windows outlined in the [Schedule of Assessments](#) as possible. An infusion may be skipped (ie, ‘missed’) or delayed at the discretion of the investigator to evaluate and treat an AE before the next infusion. The time window between each infusion may be extended as long as the last infusion of investigational product is given within 30 days of infusion 1 and the minimum window between infusions is at least 5 days.

Refer to the study reference manuals for detailed instructions for how to address study procedures performed in the Active Treatment Period and for detailed instructions for skipped (ie, ‘missed’) or delayed infusion.

Before infusion 2, dosing eligibility depends on timing of infusion 1 relative to IV contrast administration in the subsets of subjects as follows:

- For subjects who received infusion 1 of investigational product > 12 hours and < 48 hours after IV contrast administration, a local laboratory serum creatinine value must be obtained before the infusion for comparison with the local laboratory baseline value and reviewed by the investigator. A blood sample for local laboratory testing to assess dosing eligibility for infusion 2 should not occur earlier than 72 hours following infusion 1 (refer to [Section 4.2.2.2](#) for dosing eligibility).

- For subjects who received infusion 1 of investigational product  $\geq$  48 hours after FMC or IV contrast administration, eligibility for dosing will be determined by the investigator based on clinical assessment (eg, assessments of hemodynamic status, directed physical exam if clinically indicated, and AE assessment) with support of local and central laboratory serum creatinine values at baseline (refer to [Section 4.2.2.2](#) for dosing eligibility).

Before infusions 3 and 4, eligibility for dosing will be determined by the investigator based on clinical assessment (eg, assessments of hemodynamic status, directed physical exam if clinically indicated, and AE assessment) with support of available local and central laboratory serum creatinine values at baseline and follow up (refer to [Section 4.2.2.2](#) for dosing eligibility).

Before the start of infusions 2, 3, and 4, perform the following assessments:

- Prior / concomitant medication review.
- Prior laboratory value review (see footnote M in the [Schedule of Assessments](#)).
- Vital signs.
- Infusions 2 and 3 only: blood sample for central laboratory testing (biochemistry panel).
- AE / SAE monitoring.
- MACE endpoint assessment.

Administer the IV infusions 2, 3, and 4 of investigational product (placebo or CSL112) ([Section 6.2](#)).

At the end of the infusion, perform the following assessments:

- AE / SAE monitoring.
- MACE endpoint assessment.
- Infusion 4 only: blood sample for PK / PD assessment (at selected sites).

### **8.5.2.3                    Visit 6 (End of Active Treatment Period)**

- Visit 6 (Day 29) is the end of the Active Treatment Period and should occur approximately 7 ( $\pm$  2) days after infusion 4 (or last infusion) of investigational product.
- Prior / concomitant medication review.
- Vital signs.
- Body weight.

- Directed physical examination.
- Pregnancy test (if applicable).
- Blood sample for central laboratory testing (biochemistry panel and hematology, immunogenicity, and parvovirus testing).
- AE / SAE monitoring.
- MACE endpoint assessment.
- Blood sample for FBR (if subject consented).

### **8.5.3 Visits 7, 8, 9, 10, and 11 (Follow-up Period)**

Visit 7 and Visit 10 assessments may be conducted either by telephone contact or face-to-face at the study site. Visit 8, 9, and 11 assessments should be conducted face-to-face at the study site.

- Concomitant medication review of all treatments for ACS including the dose, route of administration, and frequency must be collected and monitored for change through to the EOS (Day 365). Note: All other concomitant medications taken or administered during the study will be collected through Visit 8 (Day 90), or beyond in the event of an SAE, or AEs considered related to investigational product, leading to discontinuation of investigational product, and / or leading to withdrawal of consent during the study.
- MACE endpoint assessment (all visits).
- Body weight (Visits 8, 9, and 11).
- Lifestyle adherence assessment (Visits 8, 9, and 11).
- AE monitoring (Visits 7 and 8). Note: AEs considered related to investigational product, leading to discontinuation of investigational product, and / or leading to withdrawal of consent during the study are also to be collected at Visits 9, 10, and EOS.
- AEs related to investigational product / SAE monitoring (all visits).
- EQ-5D-3L assessment (Visit 8).

### **8.5.4 Early Termination Visit**

Subjects who prematurely discontinue infusion(s) of investigational product are to be assessed at Visit 6 / Early Termination Visit as soon as possible after discontinuation of investigational product. Refer to [Sections 4.3.1](#) and [4.3.3](#) for definition of discontinuation of treatment and / or subject withdrawal from study, respectively, and [Sections 4.3.4](#) and [4.3.5](#) for follow-up procedures.

**9 Adverse Events****9.1 Definitions****9.1.1 Adverse Event**

As per the ICH guidelines, an AE is any untoward medical occurrence in a patient or clinical investigation subject administered a pharmaceutical product and which does not necessarily have a causal relationship with this treatment. An AE can, therefore, be any unfavorable and unintended sign (including an abnormal, clinically significant laboratory finding), symptom, or disease temporally associated with the use of a medicinal (investigational) product, whether or not considered related to the medicinal (investigational) product.

Adverse events may include:

- Exacerbation (ie, an increase in the frequency or severity) of a preexisting condition.
- A clinical event occurring after consent but before investigational product administration.
- Intercurrent illnesses with an onset after administration of investigational product.

Adverse events do not include:

- Events identified at screening that meet exclusion criteria.
- Medical or surgical procedures (the condition that leads to the procedure is the AE).
- Situations where an untoward medical occurrence has not taken place. For example:
  - Planned hospitalizations due to preexisting conditions, which have not worsened.
  - Hospitalizations that occur for procedures not due to an AE (eg, cosmetic surgery).
  - Hospitalizations for a diagnostic procedure where the hospital stay is less than 24 hours in duration or for normal management procedures (eg, low dose chemotherapy for a rheumatologic disorder).
  - Overdose of investigational product or any concomitant therapy that does not result in any AE signs or symptoms.

For laboratory safety parameters, any instances of absolute values being outside the reference range or changes at any visit after study start that are considered by the investigator as clinically significant must be recorded in the eCRF as AEs. In addition, at the investigator's discretion, any changes or trends over time in laboratory parameters can be recorded in the eCRF as AEs if such changes or trends are considered to be clinically relevant, even if the absolute values are within the reference range.

Laboratory findings do not need to be reported as AEs in the following cases:

- Laboratory parameters already beyond the reference range at screening, unless a further increase / decrease can be considered an exacerbation of a preexisting condition.
- Abnormal laboratory parameters caused by mechanical or physical influences on the blood sample (eg, in vitro hemolysis) and flagged as such by the laboratory in the laboratory report.
- Abnormal parameters that are obviously biologically implausible (eg, values that are incompatible with life or outside the measuring range).
- An abnormal laboratory value that cannot be confirmed after repeat analysis, preferably in the same laboratory (ie, the previous result could be marked as not valid and should not necessarily be reported as an AE).

### **9.1.2 Adverse Events of Special Interest**

Adverse events of special interest will include hypersensitivity, potential hepatic injury, AKI, and new or worsening of pre-existing HF. Potential hepatic injury and new or worsening of pre-existing HF will be adjudicated by the CEC ([Section 3.7.4](#)). At each scheduled study assessment, the investigator or a medically qualified delegate will specifically inquire about any AEs that might have occurred since the last infusion. All AEs will be recorded on the AE page of the eCRF page.

The reporting requirements for AEs of Special Interest are detailed in [Section 9.6.2](#).

#### **9.1.2.1 Hypersensitivity**

Hypersensitivity findings may include allergic reactions, bronchospasm / wheezing, generalized rash, swelling, hives, involvement of the mucous membranes, anaphylaxis, etc. Study site personnel who are medically qualified to recognize and treat hypersensitivity reactions must be available together with medications and equipment to treat such reactions.

In the event that a subject experiences signs or symptoms of a hypersensitivity reaction requiring hospitalization or urgent intervention, or there is suspected angioedema during (or within 6 hours following) an infusion of investigational product, the current infusion and all subsequent infusions must be immediately discontinued. The subject must receive immediate medical assessment and indicated supportive management per the institutional standard of care. In the event that a subject experiences an SAE of hypersensitivity, or there is suspected angioedema during infusion of investigational product, assessments should be performed as detailed in [Section 8.1.3.1.1.1](#).

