### **Apolipoprotein A-I**

---

There is potential for allergic reactions or hypersensitivity to CSL112 in certain individuals, given the constituents of the product. CSL112 consists of apoA-I purified from human plasma that may contain IgA and PC derived from soy beans. Therefore, investigators should ensure that subjects do not have a positive history of IgA deficiency or antibodies to IgA and that the subjects are not allergic to either soy bean or peanuts (there is a documented risk of cross reactions to soy in known peanut allergy sufferers).

Regarding placebo, the albumin prescribing information contains warnings for allergic and anaphylactic like reactions and notes hypersensitivity reactions under adverse reactions. The reported rate of anaphylaxis cases is very low. In addition, there has been no correlation between increasing strength and anaphylactic reaction. Due to limited data available for dosage, no trend of the association between dose and anaphylactic reaction can be made.

In the event that a subject experiences signs or symptoms of a hypersensitivity reaction requiring hospitalization or urgent intervention, or there is suspected angioedema during infusion of investigational product, the current infusion and all subsequent infusions must be immediately discontinued. The subject must receive immediate medical assessment and indicated supportive management per the institutional standard of care ([Section 9.1.2.1](#)).

If a subject experiences a serious adverse event (SAE) of hypersensitivity reaction within 72 h of administration of a dose of investigational product, or there is suspected angioedema during infusion of investigational product, additional doses of investigational product should not be administered.

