### **8.1.3.1.1 Adverse Events of Special Interest**

#### **8.1.3.1.1.1 Hypersensitivity**

In the event that a subject experiences an SAE of hypersensitivity, or there is suspected angioedema during infusion of investigational product (as defined in [Section 9.1.2](#)), the current infusion and all subsequent infusions must be immediately discontinued. The subject must receive immediate medical assessment and indicated supportive management per the institutional standard of care.

- Additional assessments are to be performed as outlined below. A follow-up is required until resolution of the event. The following assessments should be performed: Collect blood samples for complete blood count with differential ([Table 3](#)), levels of quantitative immunoglobulins (immunoglobulins G, M, E, and A), and presence of anti-IgA antibodies.
- A blood sample for immunogenicity testing will be taken as close as possible to the event and tested for anti-CSL112 and anti-apoA-I antibodies.
- The subject should be re-queried to confirm the absence of a history of allergy to soy or peanuts.
- Pertinent positives and negatives should also be assessed and documented in the source document and eCRF including but not limited to: rash, swelling, hives, itching, shortness of breath, wheezing, stridor, and involvement of the mucous membranes.
- Relevant physical examination findings should also be documented (eg, maculopapular rash, swelling of the face or oropharynx, wheezing, etc.).

Any hypersensitivity reaction should be recorded as an AE ([Section 9.6.1](#)).

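### Protocol Section 9.1.2.1 ends dosing for suspected angioedema up to 6 hours after an infusion, but Sections 7.1 and 9.6.2.1 state the same mandatory stop only for angioedema while the infusion is running

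*Protocol*

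**What the plan says.** Four protocol sections say when suspected angioedema ends dosing.

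- **Section 9.1.2.1** applies where "there is suspected angioedema during (or within 6 hours following) an infusion of investigational product", and the consequence is that "the current infusion and all subsequent infusions must be immediately discontinued". Two sentences later, the trigger for follow-up assessments loses the extension: "or there is suspected angioedema during infusion of investigational product, assessments should be performed as detailed in" Section 8.1.3.1.1.1.
- **Section 7.1** states the rule twice. The first statement reads "there is suspected angioedema during infusion of investigational product, the current infusion and all subsequent infusions must be immediately discontinued". The second reads "there is suspected angioedema during infusion of investigational product, additional doses of investigational product should not be administered", and sits beside a separate bar on further doses after an SAE of "hypersensitivity reaction within 72 h of administration of a dose of investigational product".
- **Section 9.6.2.1** repeats the words of the first Section 7.1 statement. It then requires SAE reporting within 24 hours, and the work-up, for angioedema with the same narrow timing.
- **Section 8.1.3.1.1.1** has the narrow timing with a pointer attached: "or there is suspected angioedema during infusion of investigational product (as defined in" Section 9.1.2).

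Two further places concern antibody testing. Protocol Section 8.1.3.6 analyses samples after an SAE of hypersensitivity, or after suspected angioedema while the infusion runs. SAP Section 4.6.1.2 calls for assay after a serious hypersensitivity reaction or after angioedema, with no timing condition.

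**The concern.** This is a mandatory stopping rule, and its time window depends on which section a site opens. Section 7.1, which covers precautions to further dosing, is a natural place to look and does not contain the 6 hours. Infusions 2 to 4 may be given to outpatients (Section 6.2), so onset after the infusion has finished is a realistic situation. With approximately 1000 planned sites and no statement of which section prevails, similar reactions could lead to different dosing decisions, different reporting and different laboratory work-up. A site relying on Section 7.1 could give an infusion that Section 9.1.2.1 forbids.

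**Working it through.** No arithmetic applies. The check sets the passages side by side and then follows one case through them.

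| Place | Timing of suspected angioedema | What follows |
|---|---|---|
| Protocol 9.1.2.1, stopping | During, or up to 6 hours after | Mandatory stop, all infusions |
| Protocol 9.1.2.1, work-up | During only | Assessments in 8.1.3.1.1.1 |
| Protocol 7.1, first statement | During only | Mandatory stop, all infusions |
| Protocol 7.1, second statement | During only | No additional doses |
| Protocol 8.1.3.1.1.1 | During, with pointer to 9.1.2 | Mandatory stop and assessments |
| Protocol 9.6.2.1, stopping | During only | Mandatory stop, all infusions |
| Protocol 9.6.2.1, reporting | During only | SAE report in 24 hours, assessments |
| Protocol 8.1.3.6 | During only | Antibody analysis |
| SAP 4.6.1.2 | No limit | Antibody assay |

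On stopping, one section has the wide window (9.1.2.1), two have the narrow one (7.1 and 9.6.2.1), and one is ambiguous (8.1.3.1.1.1).

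**Where the infusion ends.** Section 6.2 fixes the end of infusion at the end of the saline flush. The narrow wording therefore has a sharp edge and cannot be stretched to the hours that follow.

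**A case in the gap.** Take suspected angioedema starting 2 hours after the flush that meets no seriousness criterion and needs neither hospitalization nor urgent intervention.

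- Section 9.1.2.1: permanent stop required.
- Sections 7.1 and 9.6.2.1: stop not triggered.
- Section 8.1.3.1.1.1: depends on whether the pointer brings in the 6 hours.
- Work-up under 9.1.2.1 and SAE reporting under 9.6.2.1: not triggered.
- Antibody testing: not triggered by Protocol 8.1.3.6, but called for by SAP 4.6.1.2.

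**More serious cases at the same 2 hours.**

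- If the reaction needs hospitalization or urgent intervention, 7.1, 9.1.2.1 and 9.6.2.1 all stop dosing through that separate trigger.
- If it is an SAE, 8.1.3.1.1.1 stops dosing, and 7.1 bars further doses through its 72-hour rule. The SAE triggers for work-up, reporting and antibody testing are also met.

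The sections give different results only for the first kind of case.

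**The case against.** The best reply is that the rules add up. Sections 7.1 and 9.6.2.1 say what happens when angioedema occurs during an infusion; neither says dosing may go on when it occurs afterwards. A site applying every section would apply 9.1.2.1 and stop, and Section 4.3.1 lets the investigator stop for safety at any time. This is a fair reading for stopping, but it works only for a site that reads 9.1.2.1 alongside 7.1. It does not settle SAE reporting, work-up or antibody testing, where no protocol section states the wider window.

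The other side is right to limit the point in three respects, each of which a reader might overlook.

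- **A conflict with three sections.** A reader might count 8.1.3.1.1.1 with 7.1 and 9.6.2.1. Its pointer to 9.1.2 can be read as importing the 6 hours, so it is ambiguous, not clearly opposed.
- **Every suspected angioedema between the end of infusion and 6 hours is affected.** The urgent-intervention, SAE and 72-hour triggers already cover the more serious cases. Multiplying by about 17,400 subjects and 4 infusions gives no size, because no angioedema rate is stated. Section 1.4 reports only that hypersensitivity in AEGIS-I was 3.0% on CSL112 and 2.7% on placebo, mainly rash, with no anaphylaxis.
- **Hypersensitivity ascertainment becomes inconsistent.** The documents do not support this. Section 8.1.3.1.1.1 has every hypersensitivity reaction recorded as an adverse event, Section 9.1.2 has sites ask about adverse events at each scheduled assessment, and SAP Section 11.2.2 identifies cases by a standardized MedDRA query with no timing filter. At most, the serious or non-serious label of a case in the gap could vary with how a site reads 9.6.2.1.

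**Conclusion.** The inconsistency is real and minor: wrong as written. It concerns suspected angioedema that starts after the saline flush and within 6 hours, is not an SAE, and needs neither hospitalization nor urgent intervention. For that case the sections disagree on permanent discontinuation, and the protocol's reporting, work-up and antibody triggers do not match its widest stopping rule. The SAP's assay rule differs again.

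The number of such cases cannot be estimated from the documents. Recording of hypersensitivity adverse events is unaffected, as are the primary endpoint, power and alpha.

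The conclusion rests on two readings: that the timing phrase in 7.1 and 9.6.2.1 qualifies angioedema alone and not the urgent-intervention trigger, and that the end of infusion is as defined in Section 6.2. If the timing phrase also qualified the urgent-intervention trigger, the gap would be wider than stated here.

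**What to change.** Reconcile the time window for suspected angioedema across Protocol Sections 7.1, 8.1.3.1.1.1, 8.1.3.6, 9.1.2.1 and 9.6.2.1, and align the antibody-assay text in SAP Section 4.6.1.2. Do so for stopping, SAE reporting, work-up and antibody testing alike. If any of these is meant to have a different window, say so explicitly. Stating the window once and citing it elsewhere would keep the sections aligned. Which window applies is the sponsor's clinical decision, and this review takes no position on it.

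The cost is protocol wording, the matching SAP sentence and a clarification to sites. No design quantity or efficacy analysis changes.

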### **9.1.2.2 Potential Hepatic Injury**

Hy's Law is by definition an elevation in ALT or AST  $> 3 \times \text{ULN}$  with a concomitant increase in total bilirubin that is  $> 2 \times \text{ULN}$  without initial findings of cholestasis (elevated alkaline phosphatase  $> 2 \times \text{ULN}$ ), and with no other reason found to explain the combination of these increased ALT / AST and total bilirubin findings [FDA Guidance for Industry, 2009]. For the purpose of this study, potential Hy's law cases are defined as an elevation in ALT  $> 3 \times \text{ULN}$  with a concomitant increase in total bilirubin that is  $> 2 \times \text{ULN}$  that is confirmed by repeat assessment, without initial findings of cholestasis (ie, without elevated alkaline phosphatase) and with no other reason to explain the combination of these increased ALT and total bilirubin findings. Note that elevated AST is not being used in the definition for this study because there may be increases in AST that are due to the index MI event. If any subject has elevation in ALT  $> 3 \times \text{ULN}$  with a concomitant elevation in total bilirubin  $> 2 \times \text{ULN}$  OR an elevation in ALT  $> 5 \times \text{ULN}$ , blood samples should be obtained and sent to the central laboratory within 48 to 72 hours in order to perform the assessments detailed in [Section 8.1.3.1.1.2](#). All potential hepatic injury AEs and laboratory values meeting these criteria will be sent to the CEC for adjudication ([Section 3.7.4](#)).

